8.1 Screening

The investigator or their delegate will contact the IRT when a participant enters screening.

In the case where a safety laboratory assessment at screening/baseline is outside of the range specified in the exclusion criteria, the assessment may be repeated once prior to randomization and must be completed within 3 hours of the screening period. In this case, another consent/assent would not be required and the original participant ID number assigned will be used. However, if the repeat value remains outside of the specified ranges, the participant must be captured as a screen failure.

Rescreening of a participant with a new episode of malaria who had failed screening assessments earlier in the study is allowed per investigator's discretion and/or after consultation with the sponsor. In this case, a new consent/assent would be required and new participant ID number will be used.

IRT will be recontacted after confirming that the participant fulfills all the inclusion/exclusion criteria, to get a unique medication number for the package of study treatment and the dose level to be dispensed to the participant.

8.1.1 Information to be collected on screening failures

Participants who sign an informed consent form and are subsequently found to be ineligible prior to randomization will be considered screen failures. The reason for screen failure should be recorded on the appropriate Case Report Form. The demographic information, informed consent, and Inclusion/Exclusion pages must also be completed for screen failure participants. No other data will be entered into the clinical database for participants who are screen failures, unless the participant experienced a serious adverse event during the screening phase (see [Section 10.1.3](#) for SAE reporting details). If the participant fails to be randomized, the IRT must be notified that the participant was screen failed.

Participants who are randomized and fail to start treatment, e.g. participants randomized in error, will be considered an early terminator. The reason for early termination should be recorded on the appropriate Case Report Form.

8.2 Participant demographics/other baseline characteristics

Participant demographic and baseline characteristic data to be collected on all participants and to be entered in eCRF by site personnel:

- Age
- Gender
- Body weight
- Head circumference (for children < 2 years)
- Body height
- Body temperature
- Vital signs
- Physical examination (data to be entered only in source notes)

- Neurological examination
- Other severe malaria symptoms examination
- Prior and concomitant medications
- Blood chemistry and hematology
- Urinalysis
- Pregnancy test (data to be entered only in source notes)
- Malaria blood film for parasites and gametocytes count and plasmodium species determination
- Medical history
- Triplicate 12-lead ECG

The following data are not to be assessed or entered by clinical site, these will be generated by third parties:

CCI

Investigators will have the discretion to record abnormal test findings on the medical history CRF whenever in their judgment, the test abnormality occurred prior to the informed consent signature.

8.3 Efficacy

Efficacy assessments will be based on initial parasite clearance and clinical outcome of severe malaria signs (including neurological sequelae).

8.3.1 Clinical outcome in moderately severe and severe malaria

8.3.1.1 Clinical success

Clinical success in study participants will be evaluated at various time points throughout the study. Clinical success at 48 hours is considered as a key secondary endpoint. Clinical success is a composite endpoint based on the criteria shown below ([Table 8-3](#)).

Table 8-3 Definition of clinical success in the study at any time point

Disease criteria	Clinical failure (participant meeting any of the criteria)	Clinical success (participant has to meet all criteria)
Dead or Alive	Dead [#]	Alive
Presence of asexual parasites	Yes	No
Presence of any of the key signs of severe malaria*	Yes	No

[#] Death - All in hospital deaths and malaria related deaths (as per adjudication committee) occurring after hospital discharge
 
* Key signs of Severe Malaria defined as
 
1) Altered consciousness (including prostration) – Prostration (inability to sit or drink or breast feed) or Glasgow Coma Score < 11 (in participants > 5 years of age) or a Blantyre coma score of < 3 in children (≤ 5 years)
 
2) Renal impairment – SCr ≥ 3x ULN or Absolute SCr >3mg/dL or use of Renal Replacement Therapy (RRT)
 
3) Acidosis – Plasma lactate > 4 mmol/L or Respiratory distress defined as rapid, deep and labored breathing (costal indrawing, use of accessory muscles and nasal flaring).
		

8.3.1.2 Signs of severe malaria

Participants will be monitored for the presence of the following signs of severe malaria during the entire study duration:

- Altered consciousness - Prostration or GCS < 11 for participants > 5 years / BCS < 3 for participants ≤ 5 years of age
- Renal Impairment - Serum creatinine > 3xULN or > 3 mg/dL or need for renal replacement therapy
- Acidosis - Serum lactate > 4 mmol/L
- Respiratory distress - present or absent
- Severe anemia - Hb < 5 g/dl or Hb < 7g/dl in pediatric and adults respectively or need of blood transfusion
- Jaundice - Serum bilirubin > 3 g/dl
- Hypoglycemia- plasma glucose < 40 mg/dL

8.3.1.3 Neurological assessment

Detailed neurological examination will be conducted and relevant medical history collected under the following categories to assess the extent of neurological signs and symptoms at baseline and to monitor the extent of neurological sequelae in follow-up visits:

Table 8-4 Summary of Neurological assessment

Assessment parameter		Type of information in CRF
Consciousness	Glasgow Coma Score (GCS*) for participants > 5 years Blantyre Coma Score (BCS*) for participants ≤ 5 years	Score for individual component of GCS and BCS Total GCS or BCS calculated centrally based on individual components
	Prostration	Yes or No
Cranial Nerve Palsy	4 th , 6 th and 7 th Nerve	Palsy – present or absent If present – Right or Left nerve palsy
Motor system	Posturing	Abnormal posture - Yes or No If yes, Type of posture - Decerebrate/Decorticate/Opisth otonus/ Hemiplegic
	Cerebellar Ataxia	Present or Absent
	Strength	Presence or absence of following - Monoplegia or Monoparesis - Hemiplegia or Hemiparesis - Quadriplegia or Quadriparesis
	Deep Tendon reflex (Biceps, Triceps, Knee and Ankle) increased	Yes or No
	Increased Tone (Upper Limb and Lower Limb)	Yes or No
Convulsions	Type of convulsion	Generalised/Focal/Focal with secondary generalisation
	Presence of ≥ 2 episodes of convulsions excluding febrile seizures in the last 24 hours (for baseline visit) or since last visit (for follow-up visits)	Yes or No
	Any episode of convulsion lasting ≥ 15 min	Yes or No
Sense organs (Examination more useful at time of hospital discharge and in follow-up visits)	Vision	Check both eyes individually Graded as: • Child can see • Visual impairment unilateral/bilateral • Total blindness unilateral/bilateral

Assessment parameter		Type of information in CRF
	Hearing	Check both ears individually Graded as: 
• Can hear well• Possible hearing impairment unilateral / bilateral• Total deafness unilateral/bilateral

Assessment parameter		Type of information in CRF
	Speech	To be checked only for kids > 18 months Graded as: • Normal • Speech Impairment • Unable to speak
For details of GCS and BCS refer to Section 16.6		

Detailed methodology for each of the neurological assessments will be provided in a neurological assessment manual and the relevant site staff will be trained prior to the start of the study to maintain uniform standard of neurological examination across the study sites.

Based on the results from the neurological examination of every participant, neurological sequelae will be graded by the neurological sequelae adjudication committee. Further details about grading of neurological sequelae will be mentioned in adjudication committee charter.

8.3.1.4 Other clinical outcome assessments

In addition to the composite endpoint for clinical success as defined in [Section 8.3.1.1](#), individual signs of severe malaria as defined in [Section 8.3.1.2](#) will be closely monitored and assessed throughout the study.

Furthermore, participants will be monitored for time to start oral therapy, time to hospital discharge and time to recover from prostration also to gather holistic information about the clinical outcome of participants across treatment arms.

8.3.2 Parasitemia assessment

Malaria blood films will be prepared to determine parasite counts of asexual and sexual forms of *P. falciparum* at baseline and all visits during the study. This data will be used to assess parasite reduction or reappearance over entire study duration. Primary endpoint of proportion of participants with at least 90% *P. falciparum* parasite reduction at 12 hours is based on this assessment as well as a number of secondary endpoints related to parasitological response and parasite reduction or clearance.

Details of all parasitemia related assessments are outlined in respective manual. Quality checks of parasite readings will be part of the process.

Blood samples for molecular diagnostic purposes

Blood will be sampled for parasite genotyping as indicated in the assessment schedule ([Table 8-1](#) and [Table 8-2](#)).

At screening, a blood sample will be collected in all participants fulfilling eligibility criteria for inclusion in the study. A second blood sample will be analyzed only in participants with re-appearance of parasites. This will allow to distinguish between recrudescence and a new infection. Sample analysis will be performed at a pre-selected reference laboratory.

Microscopic identification of *Plasmodium* species might be confirmed with PCR-based methods on blood samples collected at relevant time points.

All parasite samples at baseline and other selected time points including re-appearance of parasites will also be screened for specific genes/single-nucleotide polymorphisms (SNPs) that are known as markers for *P. falciparum* drug resistance.

During the analysis process no human DNA will be amplified or analyzed by any means.

8.3.3 Appropriateness of efficacy assessments

Parasite count is a standard assessment in malaria studies as it allows to quantify the efficacy of the study drug in eliminating the parasites. In this study parasite reduction $\geq 90\%$ at 12h is used as the primary endpoint as it is expected to allow differentiation between IV cipargamin and IV artesunate.

The composite clinical endpoint is used in this study for the first time. It is a secondary endpoint and if it is demonstrated to capture the patient's clinical course appropriately might be used as primary endpoint in phase III studies. Previous studies in severe malaria have used mortality-based endpoints. Through these studies the current standard of care (IV artesunate) has been established and generally demonstrates high efficacy. As such, a very large sample size would be required in today's situation to demonstrate statistical significance and exposing large numbers of patients to an investigational treatment is not considered appropriate. Additionally, mortality as an endpoint does not capture the clinical improvement of the treated patients adequately.

The individual assessment of all symptoms of severe malaria as secondary endpoints, will allow an in-depth analysis of the drug efficacy.

8.4 Safety

Safety assessments to be conducted in the study include:

- Physical examination
- Vital signs
- Height and weight (including Head circumference of children < 2 years)
- Laboratory evaluations
- ECG evaluations
- Pregnancy assessment

For details on AE collection and reporting, refer to [Section 10.1](#).

8.4.1 Physical Examination

A complete physical examination will include the examination of general appearance, skin, neck (including thyroid), eyes, ears, nose, throat, lungs, heart, abdomen, back, lymph nodes, extremities, vascular, and neurological assessment.

Information for all physical examinations must be included in the source documentation at the study site. Clinically relevant findings that are present prior to signing informed consent must be recorded on the appropriate CRF that captures medical history. Significant findings made

after signing informed consent that meet the definition of an Adverse Event must be recorded as an adverse event.

8.4.2 Vital signs

Vital signs will include systolic and diastolic blood pressure, temperature, pulse rate, and respiratory rate as per [Table 8-1](#) and [Table 8-2](#). After the participant has been still for five minutes (as much as possible), systolic and diastolic blood pressure will be measured three times using a standard device, with an appropriately sized cuff. Repeat measurements will be made at 1-2 minute intervals and the mean of the three measurements will be used.

Temperature will be taken using a standard thermometer, for 5 minutes before reading.

8.4.3 Height and Weight

Height in centimeters (cm) and body weight (to the nearest 0.1 kilogram (kg) in indoor clothing, but without shoes) will be measured as specified in [Table 8-1](#) and [Table 8-2](#).

For children < 2 years, head circumference will be measured at baseline and study completion.

8.4.4 Laboratory evaluations

The following laboratory assessments will be performed as per the schedule mentioned in [Table 8-1](#) and [Table 8-2](#). Details of the assessments are mentioned below in [Table 8-5](#).

Clinically significant abnormalities must be recorded as either medical history/current medical conditions or adverse events as appropriate.

Table 8-5 Details of Laboratory Assessments

Test Category	Test Name
Hematology	Hemoglobin, hematocrit, red cell count (RBC and reticulocytes), white blood cell (WBC) count with differential (absolute value preferred, percentages are acceptable) (Basophils, Eosinophils, Lymphocytes, Monocytes, Neutrophils, Bands, Other), and platelet count to be assessed from point of care device. In case of non-availability of the point of care device due to any reason, local laboratory evaluation is preferred.
Chemistry	Albumin, Alkaline phosphatase (ALP), ALT (SGPT), AST (SGOT), Bicarbonate, Direct Bilirubin (DBIL), Bilirubin (TBIL), Blood urea nitrogen (BUN), Calcium, Creatinine, eGFR, Potassium, Glucose, Lactate and Sodium from point of care device. LDH, INR at local laboratory. In case of non-availability of the point of care device due to any reason, local laboratory evaluation is preferred.
Urinalysis	Macroscopic Panel (Dipstick) (Color, Bilirubin, Blood, Glucose, Ketones, Leukocytes esterase, Nitrite, pH, Protein, Specific Gravity, Urobilinogen) To be assessed at locally
Additional tests	CCI
Pregnancy Test	Serum pregnancy test to be assessed at locally (via serum pregnancy kits, if not available then as local laboratory)

8.4.5 Electrocardiogram (ECG)

ECGs should be taken in triplicate within 5 minutes (after 10 minutes rest in the supine position to ensure a stable heart rate according to the ECG investigator manual) for participants in Cohorts 1-3. For participants in Cohorts 4-5 ECG should be taken in the supine position if feasible and in triplicates if possible. The preferred sequence of cardiovascular data collection during study visits is ECG collection first, followed by vital signs, and blood sampling. For assessments where PK samples are required at 2 mins post drug administration then in those instances after drug administration, first PK sample will be collected followed by ECG, vital signs and then remaining blood sampling.

Heart rate-corrected QT interval (QTc) should be calculated by using both Fridericia's and Bazett's QT correction formula (QTcF and QTcB, respectively). Fridericia formula (QTcF) should be used for making clinical decisions.

Triplicate 12 lead ECGs are to be collected with ECG machines supplied by the central laboratory. Initial manual readout will be done locally in order to detect significant safety findings and allow for immediate response if needed. Local readout will be used for inclusion/exclusion purposes as central readout is not available within 3 hours.

In the event that a clinically significant ECG abnormality is identified at the site (e.g., severe arrhythmia, conduction abnormality of QTcF > 500 ms) the SAE must be reported according to the procedure described in [Section 10.1.2](#). If the participant is hemodynamically compromised, the investigator or a medically qualified person must initiate appropriate safety procedures without delay (for example cardioversion).

If QTcF is > 500 ms or QTcF increases ≥ 60 ms from baseline occur at any time, the participant should be assessed at the site and appropriate safety procedures (e.g., blood sampling and electrolyte correction) initiated without delay, as required. In addition, two additional ECGs should be collected at 2 min intervals and provided to the central ECG laboratory for confirmation.

Clinically significant abnormalities must be recorded on the relevant section of the medical history/Current medical conditions / AE eCRF page as appropriate.

Any post-dose average QTcF > 500 ms will result in treatment discontinuation (for details refer to [Section 6.2.1](#) and [Section 9.1.1](#)).

Assessments will be done as indicated in the study assessment [Table 8-1](#) and [Table 8-2](#). All ECGs will be assessed centrally by an independent and blinded (with age of participant identified) cardiologist.

8.4.6 Pregnancy

All pre-menopausal female participants who are not surgically sterile will have pregnancy testing as per [Section 8.1](#). Serum pregnancy test will be performed at screening and at the end of the study. If the screening serum pregnancy test is positive, the participant will not be enrolled in the study. Additional pregnancy testing might be performed if required locally. If during the study, the participant is found to be pregnant, the participant must contact the investigator immediately and study treatment will be discontinued (see details in [Section 9.1.1](#)).

Pregnancy test and associated results will not be collected on the CRF.

Participants of child-bearing potential are defined as all women physiologically capable of becoming pregnant. This includes female pediatric participants who are menarchal or become menarchal during the study.

The required contraception methods and their duration for women participants are described under exclusion criteria.

For sexually active male participants also follow recommendation as per [Section 5.2](#) under exclusion criteria.

8.4.7 Appropriateness of safety measurements

8.5 Additional assessments

8.5.1 Pharmacokinetics

PK samples will be collected at the visits defined in the assessment schedule ([Table 8-1](#) and [Table 8-2](#)). Follow instructions outlined in the laboratory manual regarding sample collection, numbering, processing and shipment. See the potential use of residual samples for more information.

In order to better define the PK profile, the timing of the PK sample collection may be altered based on emerging data.

Pharmacokinetic (PK) samples will be obtained and evaluated in all participants randomized to cipargamin (KAE609).

The parent drug concentration in plasma samples will be determined by a validated LC-MS/MS method; the anticipated Lower Limit of Quantification (LLOQ) is 1 ng/ml or better.

Concentrations will be expressed in mass per volume units and will refer to the free base.

Concentrations below the LLOQ will be reported as “zero” and missing data will be labeled as such in the Bioanalytical Data Report.

For standard pharmacokinetic abbreviations and definitions, see the list provided at the beginning of this protocol.

The following pharmacokinetic parameters will be determined using the actual recorded sampling times and non-compartmental method(s) with Phoenix WinNonlin (Version 6.4 or higher) wherever possible: C_{max} , T_{max} , AUC_{last} , AUC_{inf} , AUC_{0-t} , and $T_{1/2}$ from the plasma concentration-time data. In case of sparse sampling, summary statistics of concentrations-time data will be listed.

The linear trapezoidal rule will be used for AUC calculation. Regression analysis of the terminal plasma elimination phase for the determination of $T_{1/2}$ will include at least 3 data points after

C_{\max} . If the adjusted R^2 value of the regression analysis of the terminal phase is less than 0.75, no values will be reported for $T_{1/2}$, AUC_{\inf} and CL/F .

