admission. Participants will be hospitalized under close supervision for at least 72 hours after start of IV treatment and until oral treatment with Coartem has been initiated. Hospitalization can be extended, if needed, for participants based on disease signs, until IV treatment has been completed and oral treatment with Coartem has been initiated. All participants should be followed up until Day 29. Visits to assess safety and efficacy will be scheduled during the follow-up period as described in the assessments schedule ([Table 8-1](#), [Table 8-2](#)). If malaria symptoms re-emerge outside the scheduled study visits or any other adverse events occur, participants will be instructed to contact the investigator. Study design and assessments will slightly vary between cohorts, details are captured in [Section 5](#) and [Table 8-1](#), [Table 8-2](#). The safety of the entire study will be monitored by a Data Monitoring Committee (DMC) and stopping criteria (based on safety and lack of efficacy criteria) are in place throughout the study ([Table 3-1](#)). Recruitment in any treatment arms with cipargamin (KAE609) will be paused if stopping criteria are met. In event of recruitment pause, all relevant data will be reviewed in an ad-hoc DMC meeting and the next steps to be taken with the relevant IV cipargamin dose will be decided by Novartis based on the DMC's recommendation. Planned DMCs will occur at the end of Cohort 2 and at the end of Cohort 4. Additional DMC meetings may be conducted depending on the need.

Participants in all cohorts will be closely monitored through parasitological, biochemical, hematology, physical and neurological examinations ([Table 8-1](#), [Table 8-2](#) and [Section 8.3.1](#)). Rich PK sampling will be done in Cohorts 1 - 3 and sparse PK sampling will be done in Cohorts 4-5 for IV cipargamin participants.

Stopping criteria for the study

Data related to participant's efficacy and safety will be continuously monitored by the sponsor. If participants randomized to any IV cipargamin arms meet either the safety criteria or lack of efficacy criteria as listed in [Table 3-1](#) below, the study may be paused and a DMC review conducted.

Table 3-1 Criteria to temporarily pause the recruitment and initiate DMC review

Cohorts with planned recruitment	Number of participants meeting the safety criteria*	Number of participants meeting the lack of efficacy criteria**
Cohort with 6 participants	2	2
Cohort with 14 participants	2	2

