⁴ EOS = End Of Study (D29) OR PSW = Premature Study Withdrawal (to be performed at last visit of the participant getting discontinued from the study)

⁵ D1 - 0 H is randomization visit.

⁶ Prior to start of any study procedure.

⁷ Sample to be collected pre-dose.

⁸ Refer modified WHO Table 16-6 in Section 16.4 for detailed assessments.

⁹ INR sample to be collected at pre-dose but only to be analyzed when participant is randomized. Follow-up post baseline samples should only be collected when required as per protocol during elevated lab parameters (refer Section 16.1) LDH to be collected at pre-dose and D8, and only to be analyzed when hemoglobin is decreased by $\geq 10\%$.

¹⁰ ECG's should be taken in triplicate within 5 min after resting for at least 10 min in the supine position however only if supine is feasible and triplicates possible. Last ECG should be taken 24 hours after final IV drug dose. Pre-dose ECG can be taken in less than 30 mins before first dosing and all post baseline ECG assessments (D2 and D2 onwards) should be taken in less than 15 min post-dose.

¹¹ ECG assessment after drug administration.

¹² For all Cipargamin (KAE609) participants only.

¹³ For all Cipargamin (KAE609) participants only. Sparse PK collection with 0.5 ml blood. Missed PK sampling time should be taken as soon as possible and actual time should be recorded. For scheduled time: Pre-dose samples (24h and 48h) should be taken in less than 15 min before the dosing; Day 1: 2 min: + 1 min; 60 min: ± 10 min

¹⁴ [REDACTED]

¹⁵ [REDACTED]

¹⁶ [REDACTED]

¹⁶ Body height at the end of the study to be measured only for children participants < 2 years of age.

¹⁷ Head circumference should be measured only for children participants < 2 years of age.

¹⁸ Minimum and maximum duration of IV cipargamin will be 24 H (2 doses) and 48 H (3 doses). If cipargamin participants requires IV therapy beyond 3 doses, refer rescue medication criteria (Section 6.2.1). Minimum and maximum duration of IV artesunate will be 24 H (3 doses) and 7 D (8 doses).

¹⁹ Day 1, 12 h dosing only for participants receiving IV artesunate.

²⁰ First timepoint to switch from IV therapy to oral therapy is at 48 H. If participant is eligible, administer Coartem as per label. However, if participant is not able to tolerate oral therapy then continue with IV treatments and evaluate again at D4 and every 24 H until participant receives oral therapy.

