2.9 Pharmacokinetic endpoints

Only cipargamin pharmacokinetics will be determined in this study.

PK parameters such as AUC_{inf}, AUC_{last}, AUC_{0-t}, C_{max}, C_{2min}, T_{max}, T_{1/2}, CL/F, and V_z are determined using non-compartmental method(s) and will be used for the analysis of PK.

Summaries of PK concentrations will be provided by cohort, treatment, and visit. PK concentrations below the limit of quantification (LLOQ) will be treated as zero in summary statistics and for geometric related mean and CV, concentrations below LLOQ will be included as half of the LLOQ value. Descriptive statistics of pharmacokinetic parameters will include arithmetic and geometric means, standard deviation (SD), coefficient of variation, (CV %), median, minimum and maximum, etc. CV% geo-mean will be calculated using this formula; (sqrt (exp (variance for log transformed data)-1))*100.

Two-sided 90% confidence intervals for the mean or geometric mean will be calculated by cohort and treatment group using normal or log-normal approximation as appropriate.

For those treatment groups that are selected for Cohorts 3-5, PK analysis will be provided by treatment group using all pooled Cohorts (1-5) as well as separately pooled Cohorts 3-5. When data from different cohorts are pooled, an IV cipargamin regimen in Cohorts 3 to 5 (aged < 12 years) will be analyzed together with the equivalent IV cipargamin regimen as used in Cohorts 1 and 2 (aged ≥ 12 years).

The pharmacokinetic parameters will also be listed by cohort, treatment and patient.

AAG

α -1-acid glycoprotein (AAG) data will be collected only for patients randomized to cipargamin. Summary statistics including geometric mean will be provided by visit, cohort and pooled cohorts also. The relationship between cipargamin exposure and AAG will be explored graphically using scatter plot including the regression line for cipargamin exposure on AAG. Scatter plot for cipargamin PK parameters and AAG will be provided by cohort and pooled. Listing will be provided by cohort, patient and visit.

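### SAP 2.9 pools non-compartmental AUC, CL and Vz over cohorts whose sparse sampling cannot supply them, and does not say which cohorts enter each pooled row

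*Protocol*

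**What the plan says.** **Sampling.** Protocol Section 3 states: "Rich PK sampling will be done in Cohorts 1 - 3 and sparse PK sampling will be done in Cohorts 4-5". Table 8-2, footnote 13, describes the Cohort 4-5 schedule as "Sparse PK collection with 0.5 ml blood", with Day 1 windows "Day 1: 2 min: + 1 min; 60 min: ± 10 min" and then "Pre-dose samples (24h and 48h) should be taken in less than 15 min before the dosing". SAP Table 5-9 maps the same four times. For the first dose, Table 8-1 gives Cohorts 1-3 a pre-dose sample and samples at 2 min, 10 min, 1, 4, 12 and 24 h.

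**Protocol rules (8.5.1).** Non-compartmental parameters are derived where possible. For the sparse case: "In case of sparse sampling, summary statistics of concentrations-time data will be listed". For AUC: "The linear trapezoidal rule will be used for AUC calculation". The half-life regression needs at least three points after Cmax. If the adjusted R-squared "value of the regression analysis of the terminal phase is less than 0.75, no values will be reported for" half-life, AUCinf and CL/F. Vz is not in that list, although Table 2-1 names it among the secondary PK parameters and Table 12-4 ties it to the terminal slope.

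**SAP 2.9.** AUCinf, AUClast, AUC0-t, Cmax, C2min, Tmax, T1/2, CL/F and Vz are all said to come from non-compartmental methods. For the regimens selected for Cohorts 3-5, "PK analysis will be provided by treatment group using all pooled Cohorts (1-5) as well as separately pooled Cohorts 3-5". The sparse-sampling limit is not repeated. SAP Section 4 declares no change to the protocol's analyses.

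**The concern.** The two documents give different instructions for the youngest children. The protocol stops at concentration summaries when sampling is sparse. The SAP, which is what the programmers will follow, lists the full parameter set and pools it across cohorts that include the sparse ones. Nothing legible says which cohorts contribute to a pooled AUC, CL or Vz.

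Each way of filling the gap has a cost. If AUC is computed from the sparse profiles, a method-dependent excess is averaged with values from a denser schedule, and Cohorts 4-5 look more exposed than they are. If it is not computed, a row whose label covers ages from 6 months upward describes only older participants.

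Exposure is read elsewhere in the plan. AUC is an optional output for the DMC review after Cohort 4 (SAP Table 2-13), and SAP 2.1 allows dose similarity across cohorts to be reassessed on PK exposure at the end of the study.

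A smaller defect sits in the same section: a Vz calculated from a terminal slope rejected for poor fit may still be reported.

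**Working it through.** **1. What Cohorts 4-5 can supply.** After the 2 min peak, two samples remain before dose 2 (1 h and 24 h). After dose 2 there is one (48 h, pre-dose). The rule needs three points after Cmax, so no half-life is obtained, and hence no AUCinf, CL or Vz. Only AUC0-t and AUClast remain open. Cmax, C2min and the concentrations come from times shared with Cohorts 1-3 and are unaffected.

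**2. Direction of the bias.** After an IV bolus, a sum of declining exponentials is convex, so a straight line between two samples lies above the curve. The linear rule overstates every falling segment, and more so across a wide gap.

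**3. Size with the documents' only kinetic figure.** Protocol 4.2 gives a half-life of about 24 h. Take one compartment with C(0) = 1 and k = ln 2 / 24 = 0.02888 per h.

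- Exact AUC0-24 = (1 − 0.5)/k = 17.312.
- C(2 min) = 0.99904, C(10 min) = 0.99520, C(1 h) = 0.97153, C(4 h) = 0.89090, C(12 h) = 0.70711, C(24 h) = 0.5.
- Sparse (2 min, 1 h, 24 h): 0.0333 + 0.9524 + 16.9226 = 17.908. Ratio 17.908/17.312 = 1.034, an excess of **3.4%**.
- Rich (2 min, 10 min, 1, 4, 12, 24 h): 0.0333 + 0.1329 + 0.8195 + 2.7936 + 6.3920 + 7.2426 = 17.414. Ratio 1.006, an excess of **0.6%**.
- In the sparse case the exact area from 1 to 24 h is (0.97153 − 0.5)/k = 16.327, against 16.923 by the linear rule. The 23-hour gap therefore accounts for virtually the whole excess.

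Varying the one-compartment half-life from 12 to 36 h moves the sparse excess from 13.2% to 1.5%.

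**4. Size with a distribution phase (assumed).** Let C(t) = f·exp(−αt) + (1 − f)·exp(−kt), with the 24 h terminal half-life kept. The documents give neither f nor α, so both are varied.

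| f | distribution half-life | sparse excess | rich excess |
|---|---|---|---|
| 0.2 | 0.25 h | 4.7% | 0.8% |
| 0.3 | 1 h | 15.4% | 1.5% |
| 0.5 | 2 h | 33.2% | 3.3% |
| 0.5 | 4 h | 24.7% | 3.0% |
| 0.8 | 1 h | 90.2% | 7.2% |

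Over f from 0.2 to 0.8 and half-lives from 0.25 to 6 h, the sparse excess runs from about 5% to 90% and the rich excess from 0.8% to 8%. It is upward in every case tried.

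**5. Would a log-down rule be enough?** On the sparse times it gives 0% for one compartment. In four two-compartment cases (f = 0.3 with 1 h; f = 0.5 with 1, 2 and 4 h) it still gives 9% to 20%, where the linear rule gives 15% to 33%. It narrows the bias but does not close the gap between 1 h and 24 h.

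**6. The other reading: sparse cohorts left out.** Planned cipargamin numbers in protocol 12.8.2 are 6, 14, 38, 38 and 20 for Cohorts 1 to 5.

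- Row for Cohorts 3-5: 38/(38 + 38 + 20) = 38/96 = 40%, Cohort 3 only.
- Row for Cohorts 1-5: (6 + 14 + 38)/116 = 58/116 = 50%, Cohorts 1-3.

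**The case against.** The strongest reply is that the protocol already decides the matter. Its sparse-sampling sentence stands immediately before the trapezoidal rule, parameters are derived only where possible, and the SAP implements the protocol with no declared change. On that view no AUC is planned for Cohorts 4-5 and the bias never arises. This largely stands: omission is the expected reading under the protocol, and the bias arises only if SAP 2.9 is applied as written. It does not rescue the pooled rows, because omission is exactly what makes their labels wrong.

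Tables will show n with the cohorts side by side, so a reduced pooled count would be visible to a careful reader. That softens the labelling problem but does not replace a stated rule. Sampling times may be altered (8.5.1), and redacted sections of both documents may describe model-based exposure. SAP 2.9 itself is legible and explicitly non-compartmental.

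Two stronger readings are tempting. One is that exposure in the youngest children could be roughly doubled, an overstatement of about 105%. That needs a distribution intercept five times the terminal one, so that five-sixths of the initial concentration is lost in distribution, and nothing in the documents supports that value. The other is that the pooled rows drive paediatric dosing. No passage says so. The 5-42 µg·h/ml range in Section 3 concerns Cohorts 1-2 before study start. The range for Cohorts 3-5 comes from the richly sampled Cohorts 1-2, paediatric exposure is predicted by a population PK or PBPK model, and the pharmacokineticist checks up to 6 participants per cohort.

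**Conclusion.** The point holds as a conflict between SAP 2.9 and protocol 8.5.1 that leaves the pooled PK rows undefined. Half-life, AUCinf, CL and Vz cannot come from Cohorts 4-5 on the stated schedule and three-point rule. For AUC0-t and AUClast, the pooled rows either carry an upward bias from sparse profiles or cover 40% and 50% of the planned cipargamin participants that their labels imply.

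The bias is about 3.4% against 0.6% under a 24 h half-life and one compartment. Anything larger rests on an assumed distribution phase. The omission of Vz from the adjusted R-squared rule is a genuine but small gap. These are descriptive secondary PK summaries; the primary and key secondary efficacy analyses are not touched. The wording should still be corrected.

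**What to change.** **SAP 2.9.** Restrict non-compartmental AUC, T1/2, CL and Vz to Cohorts 1-3, and label every pooled row by the cohorts that contribute. For Cohorts 4-5, and for any pooled AUC or CL that includes them, use individual estimates from the population PK model already planned in protocol 4.2 and report shrinkage; otherwise state that no AUC is reported there. Cmax, C2min and concentrations can stay pooled as they are.

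**Protocol 8.5.1.** Use linear-up/log-down for AUC after the IV bolus. This is a modest gain on the rich schedule (from 0.6% to zero in the one-compartment case) and is not a remedy for the sparse one. Add Vz to the parameters withheld when adjusted R-squared is below 0.75.

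**Cost.** Small wording changes in both documents and one software setting. With so few samples per child, model-based estimates will shrink toward the population values, which is why shrinkage should be shown. If the redacted sections already describe the model, a cross-reference from SAP 2.9 would cover that part.
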